Treatment Cycle		1	2	3 and onwards (up to 17 cycles)	DC	Safety Follow-up ^a	Efficacy Follow-up Visits				Survival Follow-up	Procedures should occur predose on Day 1 of each cycle unless otherwise noted.
Scheduled Timing	-28 to -1				At time of DC	30 days post last dose	Q12W Year 1 from RAND	Q12W Year 2-3 from RAND	Q24W for Year 4-5 from RAND	Annually for Year 6-7 from RAND	~Q12W	Post-treatment Period: Refer to Sections 8.11.2.1, 8.11.2.2, and 8.11.2.3
Window (days):		+3	±3	±3		+7	±7	±14	±14	±14	±14	
AE=adverse event; BCLC=Barcelona Clinic Liver Cancer; BP=blood pressure; C=Cycle; C1D1=Cycle 1 Day 1; CR=complete response; CT=computed tomography; CCI=Confidential; D=Day; DC=Discontinuation; ECG=electrocardiogram; ECI=Event of Clinical Interest; ECOG=Eastern Cooperative Oncology Group; EORTC=European Organization for Research and Treatment of Cancer; EOT=End-of-Treatment; HCV=Hepatitis C virus; HIV=human immunodeficiency virus; INR=international normalized ratio; LLOD= lower limit of detection; MRI=magnetic resonance imaging; PD=progressive disease; PRO=Patient-reported Outcomes; PT=prothrombin time; Q3W=every 3 weeks; Q12W=every 12 weeks; Q24W=every 24 weeks; RAND = randomization; SAE=serious adverse event; T3=triiodothyronine; T4=thyroxine; TSH=thyroid-stimulating hormone; WOCBP=women of childbearing potential.												
a. If the EOT Visit occurs ≥ 30 days after the last dose of study intervention, a Safety Follow-up Visit is not required. In this situation, all procedures required at the Safety Follow-up Visit and EOT Visit are performed once and entered into the EOT Visit only. b. Prior scans performed within the screening period, but before signing informed consent may be used if consistent with protocol requirements per Site Imaging Manual. The same imaging technique regarding modality and the use of contrast should be used in a participant throughout the study to optimize the visualization of new tumor burden. c. Imaging at EOT is not required if the previous tumor imaging assessment was within 4 weeks prior to EOT Visit. d. In the case of hepatic ECIs, additional tests are to be performed as described in Section 6.6.2, Guidance for Management of Hepatic Events of Clinical Interest. All additional laboratory tests should be performed by a central laboratory, if possible. NOTE: For additional CCI, refer to Section 10.7.8 (Table 15).												

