6.6 Dose Modification (Escalation/Titration/Other)

6.6.1 Immune-Related Events and Dose Modification (Withhold, Treat, Discontinue)

Dose Modification and Toxicity Management for Non-hepatic Immune-related AEs Associated with Pembrolizumab

AEs associated with pembrolizumab exposure may represent an immune-related response. These irAEs may occur shortly after the first dose or several months after the last dose of pembrolizumab treatment and may affect more than one body system simultaneously. Therefore, early recognition and initiation of treatment is critical to reduce complications. Based on existing clinical study data, most irAEs were reversible and could be managed with interruptions of pembrolizumab, administration of corticosteroids and/or other supportive care. For suspected irAEs, ensure adequate evaluation to confirm etiology or exclude other causes. Additional procedures or tests such as bronchoscopy, endoscopy, skin biopsy may be included as part of the evaluation. Based on the severity of irAEs, withhold or permanently discontinue pembrolizumab and administer corticosteroids.

Dose Modification and Toxicity Management Guidelines for Non-hepatic irAEs associated with pembrolizumab monotherapy, coformulations, or IO combinations are provided in [Table 4](#).

Table 4 Dose Modification and Toxicity Management Guidelines for Non-hepatic Immune-related Adverse Events Associated with Pembrolizumab Monotherapy, Coformulations or IO Combinations

General instructions: 1. Severe and life-threatening irAEs should be treated with IV corticosteroids followed by oral steroids. Other immunosuppressive treatment should begin if the irAEs are not controlled by corticosteroids. 2. Pembrolizumab monotherapy, coformulations or IO combinations must be permanently discontinued if the irAE does not resolve or the corticosteroid dose is not ≤ 10 mg/day within 12 weeks of the last treatment. 3. The corticosteroid taper should begin when the irAE is \leq Grade 1 and continue at least 4 weeks. 4. If pembrolizumab monotherapy, coformulations or IO combinations have been withheld, treatment may resume after the irAE decreased to \leq Grade 1 after corticosteroid taper.				
irAEs	Toxicity Grade (CTCAEv4.0)	Action With Pembrolizumab Monotherapy, Coformulations or IO Combinations	Corticosteroid and/or Other Therapies	Monitoring and Follow-up

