Hepatitis B consider flare or change in HBV immunologic status	Rapid elevation of ALT to >5×ULN and/or >3× baseline	
Interrupt pembrolizumab/placebo intervention for up to 12 weeks.
 
Start antiviral therapy or check for compliance if HBV is detectable.
 
Measure safety laboratory test results for AST, ALT, ALP, T Bili, D Bili, and INR on weekly basis.
 
Measure HbsAg and HBV DNA on weekly basis (if detected at the time of onset of ECI).
 
Evaluate the following every 2-3 weeks:
 
 anti-Hbe, Hbe antigen, anti-HBs, and HBV viral load (if not detected at the onset of ECI) 
Restart pembrolizumab/placebo intervention only if ALT returns to normal or Grade 1 (if normal at baseline), or to baseline grade (if Grade 2 at baseline) within 12 weeks, and the participant is clinically stable; otherwise, the participant should be permanently discontinued.

Hepatitis C exacerbation in participants with HCV RNA positive	Rapid elevation of ALT to >5×ULN and/or >3× baseline	
Interrupt pembrolizumab/placebo intervention for up to 12 weeks.
 
Assess use of injection or inhalation drugs.
 
Recheck HCV genotype at the time of relapse of HCV viral load to rule out new infection.
 
Measure safety laboratory test results for AST, ALT, ALP, T Bili, D Bili, and INR on weekly basis
 
Measure HCV viral load every 2 weeks.
 
Please discuss risk-benefit with Sponsor prior to starting HCV antiviral therapy.
 
Restart pembrolizumab/placebo intervention only if ALT returns to normal or Grade 1 (if normal at baseline), or to baseline grade (if Grade 2 at baseline) within 12 weeks, and the participant is clinically stable; otherwise, the participant should be permanently discontinued.

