Relapse of HCV infection for participants with successfully treated or new HCV infection	If HCV RNA was TND at baseline, and now has confirmed detectable HCV RNA (2 specimens, 1 week apart)	
Interrupt pembrolizumab/placebo study intervention for up to 12 weeks.
 
Start IV corticosteroid 60 mg/day of prednisone or equivalent followed by oral corticosteroid.
 
Monitor with biweekly laboratory tests, including AST, ALT, T Bili, D Bili, ALP, and INR.
 
Restart pembrolizumab/placebo intervention only if:
 
 Abnormal laboratory values resolve to Grade ≤1 or baseline (if abnormal at baseline) Taper steroid over 28 days Steroid treatment is tapered to prednisone <10 mg/day or equivalent 
Permanently Discontinue pembrolizumab/placebo intervention if:
 
 Laboratory abnormalities do not resolve within 3 weeks Steroids cannot be lowered to ≤10 mg/day (or prednisone equivalent) within 12 weeks Decompensation to CP C status
Immune-related Hepatitis	
If any of the HECI criteria is met as defined in the protocol Section 8.4.7
 
Note:
 
Immune-related hepatitis is a diagnosis made after excluding other possible etiologies such as viral flare, biliary or vascular obstruction, infection, medications, and alcohol use usually immune-related hepatitis response to dechallenge and/or steroids and re-occurs with rechallenge
	
Interrupt pembrolizumab/placebo study intervention for up to 12 weeks.
 
Start IV corticosteroid 60 mg/day of prednisone or equivalent followed by oral corticosteroid.
 
Monitor with biweekly laboratory tests, including AST, ALT, T Bili, D Bili, ALP, and INR.
 
Restart pembrolizumab/placebo intervention only if:
 
 Abnormal laboratory values resolve to Grade ≤1 or baseline (if abnormal at baseline) Taper steroid over 28 days Steroid treatment is tapered to prednisone <10 mg/day or equivalent 
Permanently Discontinue pembrolizumab/placebo intervention if:
 
 Laboratory abnormalities do not resolve within 3 weeks Steroids cannot be lowered to ≤10 mg/day (or prednisone equivalent) within 12 weeks Decompensation to CP C status

	Diagnosis	Management

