7 DISCONTINUATION OF STUDY INTERVENTION AND PARTICIPANT WITHDRAWAL

7.1 Discontinuation of Study Intervention

Discontinuation of study intervention does not represent withdrawal from the study.

As certain data on clinical events beyond study intervention discontinuation may be important to the study, they must be collected through the participant's last scheduled follow-up, even if the participant has discontinued study intervention. Therefore, all participants who discontinue study intervention prior to completion of the protocol-specified treatment period/vaccination will still continue to be monitored in the study and participate in the study visits and procedures as specified in Section 1.3 (SoA) and Section 8.11.3 (Participants Discontinued from Study Intervention but Continuing to be Monitored in the Study) unless the participant has withdrawn from the study (Section 7.2).

Participants may discontinue study intervention at any time for any reason or be discontinued from the study intervention at the discretion of the investigator should any untoward effect occur. In addition, a participant may be discontinued from study intervention by the investigator or the Sponsor if study intervention is inappropriate, the study plan is violated, or for administrative and/or other safety reasons. Specific details regarding procedures to be performed at study intervention discontinuation are provided in Section 8.1.9.

A participant must be discontinued from study intervention but continue to be monitored in the study for any of the following reasons:

The participant or participant's legally acceptable representative requests to discontinue study intervention

AEs described in the dose modification table that require discontinuation of study intervention (refer to Section 6.6.1).

After prolonged study intervention interruption that prohibits restarting study intervention if agreed upon with the Sponsor.

The participant has a medical condition or personal circumstance which, in the opinion of the investigator and/or Sponsor, placed the participant at unnecessary risk from continued administration of study intervention.

The participant has a confirmed positive serum pregnancy test.

The participant is receiving any prohibited concomitant medication requiring withdrawal (refer to Section 6.5).

Participant has any of the following non-overdose hepatic ECIs:

- ALT $>20 \times \text{ULN}$ (confirmed within 1 week)

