- Drug-related total bilirubin $>10 \times \text{ULN}$
- CP score of >9 points
- Hepatic encephalopathy
- If ascites is not manageable by intervention within 3 days
- Gastrointestinal bleeding suggestive of portal hypertension (eg, esophageal or gastric varices)

Recurrence of either intrahepatic or extrahepatic disease.

Any progression or recurrence of any malignancy, or any occurrence of another malignancy that requires active treatment

Completion of 17 treatments (approximately 1 year) with pembrolizumab versus placebo.

Note: The number of treatments is calculated starting with the first dose.

For participants who are discontinued from study intervention but continue to be monitored in the study, all visits and procedures, as outlined in the SoA, should be completed.

Discontinuation from study intervention is “permanent.” Once a participant is discontinued, he/she shall not be allowed to restart study intervention.

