8.4.7 Events of Clinical Interest (ECIs)

Selected nonserious and SAEs are also known as ECIs and must be reported to the Sponsor.

Events of clinical interest for this study include:

1. An overdose of Sponsor's product, as defined in Section 8.5, that is not associated with clinical symptoms or abnormal laboratory results.
2. Hepatic ECIs include any of the following events if the events are considered not due to disease progression as judged by the investigator. All of these events (if not associated with disease progression under study) will require holding study treatment, notification of the event(s) to the Sponsor within 24 hours after awareness via electronic media or paper.

For dose interval modification, refer to Section 6.6.1. For guidance related to the diagnosis and management of hepatic ECIs, refer to Section 6.6.2.

- ALT:
 - Among subjects with Baseline ALT $<2 \times \text{ULN}$: ALT $\geq 5 \times \text{ULN}$
 - Among subjects with Baseline ALT $\geq 2 \times \text{ULN}$: ALT $>3 \times$ the Baseline level
 - ALT >500 U/L regardless of baseline level
- Total Bilirubin:
 - Total bilirubin >3.0 mg/dL
- Regardless of laboratory values, hepatic decompensation diagnosed clinically, including:
 - New onset clinically detectable ascites requiring intervention for >3 days

- Hepatic Encephalopathy
- Gastrointestinal bleeding

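### Section 6.6.2 allows restart after immune-related hepatitis but sets no permanent stop if it recurs; two cross-references also need correcting

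*Combined protocol and SAP*

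**What the plan says.** Hepatic events of clinical interest (ECIs) are defined in Section 8.4.7, which requires treatment to be held. It then adds: "For dose interval modification, refer to Section 6.6.1. For guidance related to the diagnosis and management of hepatic ECIs, refer to Section 6.6.2".

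Section 6.6.2 holds the hepatic interruption, restart and stop rules. Its immune-related hepatitis row interrupts treatment for up to 12 weeks and gives steroids. Restart is allowed once laboratory values are back to Grade 1 or baseline and steroids have been tapered over 28 days to below 10 mg/day of prednisone. The row lists three permanent stops: "Laboratory abnormalities do not resolve within 3 weeks"; steroid dose not brought down to 10 mg/day by 12 weeks; and deterioration to Child-Pugh C. Its diagnosis column notes that the event usually responds to stopping drug or to steroids, and comes back on rechallenge.

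Table 4 of Section 6.6.1 is titled "Dose Modification and Toxicity Management Guidelines for Non-hepatic Immune-related Adverse Events". The rest of 6.6.1 deals with infusion reactions and interruptions for other reasons.

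Section 7.1 lists mandatory discontinuations. One item reads "AEs described in the dose modification table that require discontinuation of study intervention (refer to Section 6.6.1"; another reads "After prolonged study intervention interruption that prohibits restarting study intervention if agreed upon with the Sponsor". It also has six hepatic items: ALT above 20×ULN, drug-related bilirubin above 10×ULN, "CP score of >9 points", encephalopathy, unmanageable ascites, and bleeding suggestive of portal hypertension.

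**The concern.** The protocol itself expects immune-related hepatitis to return on rechallenge and permits rechallenge, but does not say what happens after the second episode. The usual backstop, the All Other irAEs row of Table 4, is closed to hepatitis because the table excludes hepatic events. Every participant has or had HCC, many will have cirrhosis or viral hepatitis, and Table 2 admits AST and ALT up to 5×ULN. Two sites could therefore handle the same recurrence differently, one stopping for good and the other restarting a second or third time.

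The cross-references add some friction. The sentence on dose modification after a hepatic ECI names a section with no hepatic rule, and the list of mandatory stops in 7.1 does not mention 6.6.2.

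**Working it through.** The check is textual, with a little arithmetic on the ALT thresholds.

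**1. How Table 4 treats a Grade 3 event and a recurrence, against the hepatitis row.**

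| Row | First Grade 3 event | Stated recurrence stop |
|---|---|---|
| Pneumonitis | Permanent stop | Yes (recurrent Grade 2) |
| Diarrhea/colitis | Withhold | Yes (recurrent Grade 3) |
| Nephritis | Permanent stop | None |
| Myocarditis | Permanent stop (from Grade 2) | None |
| All Other irAEs | Withhold or discontinue | Yes (recurrent Grade 3) |
| Four endocrine rows | Withhold, discretion or continue | None |
| Immune-related hepatitis (6.6.2) | Hold, restart allowed | None |

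Three of the nine Table 4 rows have a recurrence stop. All five non-endocrine rows end treatment for Grade 3 toxicity either at the first event (pneumonitis, nephritis, myocarditis) or on its return (colitis, All Other). The hepatitis row does neither.

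**2. Which recurrences fall in the gap.** The clinical decompensation events in 8.4.7 largely overlap the 7.1 stops, so the gap mainly concerns recurrences defined by laboratory values. For ALT, the lower edge is the 8.4.7 criterion and the upper edge is the 20×ULN stop in 7.1:

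- Baseline below 2×ULN: from 5×ULN to 20×ULN.
- Baseline 2×ULN: above 3 × 2 = 6×ULN, to 20×ULN.
- Baseline 5×ULN (the Table 2 entry limit): above 3 × 5 = 15×ULN, to 20×ULN.
- At any baseline, the lower edge is 500 U/L if that is reached first.

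For bilirubin, the band runs from above 3.0 mg/dL to 10×ULN where the rise is drug-related. Within these bands a recurrence that recovers in time and does not reach Child-Pugh C can be followed by another restart, with no stated limit on repeats. I have not mapped the bands to CTCAE grades, because the documents do not give the cut-offs.

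**3. What else applies to a recurrence.**

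- A recurrence that meets 8.4.7 is a new hepatic ECI, so treatment is held and the same restart conditions and three stops apply again.
- Section 6.6.2 requires retreatment after a hepatic ECI to be reported and recorded.
- Section 10.3.5 requires advance Sponsor approval for rechallenge in two situations: after a serious event that the product may have caused, or where giving it again adds a potentially significant risk. That approval follows the protocol's dose modification guidelines, which have no recurrence rule for hepatitis.
- Section 7.1 allows discontinuation where the investigator or Sponsor judges that continuing places the participant at undue risk.

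None of these makes recurrence itself a mandatory stop.

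**4. The pointers.** Section 6.6.1 contains no hepatic ECI rule and no onward reference to 6.6.2. Apart from 8.4.7, the body text points to 6.6.2 only in footnote d of the Schedule of Activities, for testing: "In the case of hepatic ECIs, additional tests are to be performed as described in Section 6.6.2". Section 6.6.2 states four distinct permanent-stop conditions:

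- In the hepatitis B and C rows, restart requires ALT recovery "within 12 weeks, and the participant is clinically stable; otherwise, the participant should be permanently discontinued".
- Laboratory abnormalities unresolved at 3 weeks.
- Steroids not lowered by 12 weeks.
- Child-Pugh C.

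Only the last is in the 7.1 hepatic list, since more than 9 points is class C (10–15 points, Appendix 14). So 4 − 1 = 3 are not listed there. This count covers explicit permanent stops only; the Other Causes row has a 3-week restart limit but no such wording.

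**The case against.** Four arguments on the other side deserve weight.

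First, a reader might infer that every other recurrent immune-related event must stop, so that hepatitis is the lone exception. The documents do not support that. Six of nine Table 4 rows have no recurrence stop, and recurrent Grade 2 nephritis, for example, has none. The comparison that stands is narrower: it concerns Grade 3 toxicity in the non-endocrine rows.

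Second, a further restart is not unregulated. The hold, the recovery conditions, the 3-week and 12-week limits and the approval rule in 10.3.5 all apply again. The second approval trigger may well cover another restart after hepatitis has already come back, whether or not the event was serious. This stands and limits the risk, but it leaves the outcome to case-by-case approval.

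Third, the remark about rechallenge is in the diagnosis column, as a feature that helps identify the condition. That is so. It still shows that recurrence was foreseen, and the management column does not address it.

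Fourth, a reader might infer from the pointers that sites have no hepatic dosing rules, or that 7.1 contradicts 6.6.2. Neither follows. The adjacent sentence of 8.4.7 leads to 6.6.2 for management, which is where the interruption and restart rules stand. The 6.6.2 stops bind in their own right, and the three absent from 7.1 arise only once a hepatic event is already being managed under that table. The prolonged-interruption item in 7.1 also partly covers the 12-week limits, subject to Sponsor agreement. The pointer errors therefore have little practical effect.

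**Conclusion.** The point holds and is minor. The substantive part is that the immune-related hepatitis row permits restart without a mandatory stop on recurrence, and Table 4 cannot fill the gap because it excludes hepatic events. For ALT the gap runs from the 8.4.7 threshold, 5×ULN at low baseline, up to 20×ULN, and only for episodes that clear the restart conditions.

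The number of participants affected cannot be estimated. The documents give frequencies of immune-related hepatitis but no rate of restart or of recurrence after it, and first-event frequencies do not measure the gap.

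The pointers in 8.4.7 and 7.1 are housekeeping. Nothing here affects alpha, power, or the RFS and OS analyses. Efficacy is analyzed by intention to treat, and the primary RFS analysis counts recurrence regardless of treatment discontinuation. The conclusion rests on the visible text; the DMC charter and the manuals outside the protocol were not available.

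**What to change.** 1. In the immune-related hepatitis row of Section 6.6.2, add to the permanent-discontinuation list: *Immune-related hepatitis that again meets the hepatic ECI criteria of Section 8.4.7 after restart.* This uses the protocol's own baseline-adjusted criteria and needs no new grade cut-off.
2. In Section 8.4.7, replace the first pointer with: *For dose interruption, restart and discontinuation after a hepatic ECI, refer to Section 6.6.2.*
3. In Section 7.1, change the reference in the dose-modification item to *Sections 6.6.1 and 6.6.2*.

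No new assessments or data are needed. Items 2 and 3 have no evident downside. The cost of item 1 is that participants whose hepatitis recurs lose a further restart, including any whose event is wrongly attributed, since this is a diagnosis of exclusion made under blinding. If the Sponsor prefers to keep the option of a further restart, the row should say so and name the approval required.

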8.5 Treatment of Overdose

For this study, an overdose of pembrolizumab will be defined as any dose of 1000 mg or greater.

No specific information is available on the treatment of overdose of pembrolizumab. In the event of overdose, the participant should be observed closely for signs of toxicity. Appropriate supportive treatment should be provided if clinically indicated.

8.6 Pharmacokinetics

PK parameters will not be evaluated in this study.

8.6.1

CCI [REDACTED]

Blood should be collected predose for Cycles 1, 2, 5 and at EOT. CCI [REDACTED]

Further details are provided in the Laboratory Manual.

8.7 Pharmacodynamics

Pharmacodynamic parameters will not be evaluated in this study.

